**Confidential**

---

**Observed Case Analysis:** In the third analysis, subjects are excluded from the analysis if the subject has insufficient data to be determined as a responder or non-responder in a given 4-week assessment period. This analysis is not based on the ITT population and, therefore, interpretation of results from this analysis requires substantial caution. This is because the subjects who responded in the respective treatment groups may have different distributions for background characteristics. Thus, additional analysis may be undertaken by the use of statistical methods which provide adjustment for background characteristics.

#### **8.7.3      Interim Analyses and Data Monitoring**

No interim analyses are planned for this study.

#### **8.7.4      Multicenter Studies**

Centers will be pooled within countries for the assessment of country effects.

#### **8.7.5      Multiple Comparisons/Multiplicity**

The study has a single primary endpoint as the primary hypothesis, therefore no multiplicity adjustment is needed to the overall significance level of 0.05. Additionally, the clinical trial will be providing data for two separate indications (induction and long term treatment) with each indication having its own separate endpoint. On that basis, no multiplicity adjustment is needed to the overall significance level of 0.05 per indication because conclusions will be reached independently for induction and separately for long term treatment.

The complete evaluation of clinical efficacy in this study requires the study of multiple key secondary efficacy variables collected at numerous time points. It is therefore necessary to properly and sensitively control the probability of making erroneous conclusions based solely upon compounding the likelihood of a type I error. The issue of multiplicity of secondary measurements will be handled by statistical testing of these outcomes in a hierarchical fashion. The order of secondary endpoints for the Induction and Long Term Treatment Phases are described in Sections 2.2.2 and 2.2.3. Significance tests will be conducted until a non-significant p-value is found ( $p > 0.05$ ). Once a non-significant p-value occurred, all subsequent significance tests will be considered exploratory in nature.

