### 2.2.3 Secondary Efficacy Endpoints

- Induction of clinical remission defined as a CDAI Score of less than 150 points at Week 16.
- Clinical symptom remission over time: The total number of liquid/very soft stools for the 7 days prior to each clinic visit being  $\leq 10$ ; AND (2) an abdominal pain rating of  $\leq 1$  on each day for the last 7 days prior to each clinic visit in  $\geq 80\%$  of the study visits during the 52-Week Treatment Period, including Week 52.
- Time until durable response (see Section 8.6.2) to the liquid/very soft stool component of the co-primary endpoint during the 52-Week Treatment Period.
- Time until durable response (See Section 8.6.2) to the abdominal pain component of the co-primary endpoint during the 52-Week Treatment Period.
- Proportion of subjects with response to the abdominal pain component of the co-primary endpoint at post-baseline time points.
- Proportion of subjects with response to the liquid/very soft stool component of the co-primary endpoint at post-baseline time points.
- Change from baseline in SES-CD score at Week 16 and Week 52.
- Proportion of subjects with SES-CD score of 0 at Week 52.

Confidential

---

- Proportion of subjects who achieve clinical remission by the CDAI endpoint at post-baseline time points.
- Time to loss of CDAI response defined by a CDAI score of  $\geq 150$  points during the Long Term Treatment Phase.
- Percentage of subjects who achieve clinical response at post-baseline time points. Clinical response is defined as a reduction of at least 100 points from the baseline CDAI score.
- Time to clinical remission based on abdominal pain and liquid stool components of the co-primary endpoints.
- Time to clinical remission based on CDAI  $< 150$ .
- Change from baseline in indices of health outcomes (Inflammatory Bowel Disease Questionnaire [IBDQ], Work Productivity and Activity Impairment Questionnaire for Crohn's Disease [WPAI-CD]) at post-baseline time points.
- Change from baseline in markers of inflammation (e.g. CRP, interleukins, cytokines, fecal calprotectin) at post-baseline time points.

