### 8.2 Determination of Sample Size

The information below provides the background information for sample size determination for the induction of clinical remission with endoscopic response at 16 weeks followed by clinical and endoscopic remission at 52 weeks. For placebo, the expected rates are based on data from a Phase 2 study (RETIC 03/06) conducted in subjects with active moderate Crohn's disease. The rates for Rifaximin DR are based on the assumption that Rifaximin DR will provide a somewhat higher induction of remission rate.

Expected rates for induction of clinical remission with endoscopic response at Week 16 are 40% for placebo and 55% for Rifaximin DR.

Based on a significance level of 5% (alpha 0.05), a sample size of approximately 240 subjects per treatment group will have at least 90% power to test the hypothesis that Rifaximin DR is superior to placebo for each co-primary endpoint considered individually. Approximately 80% power is available to detect significant differences between Rifaximin DR and placebo for both co-primary endpoints.

For the Long Term Treatment Phase, a 15% treatment effect is expected for both clinical symptom and endoscopic remission at Week 52. Based on this assumption and testing at a significance level of 5% (alpha 0.05), a sample size of approximately 210 subjects per treatment group will have at least 90% power to test the key secondary efficacy hypothesis that Rifaximin DR is superior to placebo when each key co-secondary endpoint is considered individually. In addition, approximately 80% power is available to detect significant differences between Rifaximin DR and placebo for each of the key co-secondary endpoints.

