#### **8.6.1 Primary Efficacy Analysis,**

##### **Induction Phase**

There will be two co-primary measures of efficacy assessed during the Induction Phase. The first co-primary endpoint is:

- Clinical symptom remission defined by (1) the total number of liquid/very soft stools for the 7 days prior to the Week 16 visit being  $\leq 10$  (from CDAI Item 1); AND (2) an abdominal pain rating of  $\leq 1$  (from CDAI Item 2) on each day for the 7 days prior to the Week 16 visit.

The second co-primary endpoint is:

- Endoscopic response defined as a  $\geq 3$ -point decrease in the SES-CD from baseline to the SES-CD score obtained between Week 16 and Week 17. SES-CD scores will be calculated from centrally-read digital video of ileocolonoscopies performed at baseline and between Week 16 and Week 17.

For each endpoint, the null hypothesis  $H_0: \pi_R - \pi_P = 0$  versus the alternative  $H_A: \pi_R - \pi_P \neq 0$  is of interest, where  $\pi_R$  is the binomial parameter for induction of remission/response for the

Confidential

---

Rifaximin DR group, and  $\pi_P$  is the binomial parameter for induction of remission/response for the placebo group. Subjects who require the initiation of rescue medication and/or surgery for CD will be considered treatment failures from the date of the introduction of the rescue medication and/or surgery, regardless of their actual response data. The Cochran-Mantel-Haenszel (CMH) test, stratified by country, will be used to test the hypothesis. Each null hypothesis of no difference will be rejected if the resulting p-value for the respective statistical test is less than 0.05. Significance for the induction claim will only be declared if both null hypotheses are rejected. As such, the overall Type I error rate will be maintained at the 5% level without adjustment for multiple comparisons.

If it is evident that the response variable is confounded with some of the background variables, then logistic regression will be performed using the background variables as covariates. The differences between this adjusted analysis and the previous unadjusted analysis will be noted, and the impact of such differences will be discussed.

The primary efficacy analysis will be repeated on the PP population to assess the robustness of the results of the primary outcome.

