4.3 Secondary Efficacy Endpoints

- Induction of clinical remission defined as a CDAI Score of less than 150 points at Week 16.
- Clinical symptom remission over time: The total number of liquid/very soft stools for the 7 days prior to each clinic visit being ≤ 10 ; AND (2) an abdominal pain rating of ≤ 1 on each day for the last 7 days prior to each clinic visit in $\geq 80\%$ of the study visits during the 52-Week Treatment Period, including Week 52.
- Time until durable response (see Section 7.2) to the liquid/very soft stool component of the co-primary endpoint during the 52-Week Treatment Period.
- Time until durable response (See Section 7.2) to the abdominal pain component of the co-primary endpoint during the 52-Week Treatment Period.
- Proportion of subjects with response to the abdominal pain component of the co-primary endpoint at post-baseline time points.
- Proportion of subjects with response to the liquid/very soft stool component of the co-primary endpoint at post-baseline time points.
- Change from baseline in SES-CD score at Week 16 and Week 52.
- Proportion of subjects with SES-CD score of 0 at Week 52.
- Proportion of subjects who achieve clinical remission by the CDAI endpoint at post-baseline time points.
- Time to loss of CDAI response defined by a CDAI score of 150 points during the Long Term Treatment Phase.
- Percentage of subjects who achieve clinical response at post-baseline time points.
Clinical response is defined as a reduction of at least 100 points from the baseline CDAI score.
- Time to clinical remission based on abdominal pain and liquid stool components of the co-primary endpoints.
- Time to clinical remission based on CDAI < 150 .

- Change from baseline in indices of health outcomes (Inflammatory Bowel Disease Questionnaire [IBDQ], Work Productivity and Activity Impairment Questionnaire for Crohn's Disease [WPAI-CD]) at post-baseline time points.
- Change from baseline in markers of inflammation (e.g. CRP, interleukins, cytokines, fecal calprotectin) at post-baseline time points.

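### The protocol's secondary testing order cannot be run as written: several steps hold up to about 20 p-values with no pass rule, and read as one chain it puts a Week 16 endpoint behind Week 52

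*Protocol*

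**What the plan says.** Protocol 8.7.5 recognises that many secondary variables at many visits raise a type I error problem. Its answer is a hierarchy in the order of Sections 2.2.2 and 2.2.3: "Significance tests will be conducted until a non-significant p-value is found". Everything after the first p > 0.05 is exploratory.

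Section 2.2.2 holds only the Week 52 pair. Section 2.2.3 then opens with CDAI below 150 at Week 16 and continues through a list that mixes both phases. Some items are single tests. Others are not, for example: "Proportion of subjects with response to the abdominal pain component of the co-primary endpoint at post-baseline time points". The SAP repeats these items in 4.3, for example: "Proportion of subjects with response to the liquid/very soft stool component of the co-primary endpoint at post-baseline time points".

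The same protocol section also says that "conclusions will be reached independently for induction and separately for long term treatment".

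SAP 7.11 carries over the paragraph on the two indications but not the hierarchy. SAP 7.7.2.1 analyses the multi-visit binary items by the primary method, that is, by significance tests. SAP 7.7.2.4 makes all secondary endpoints descriptive if the primary endpoints are not significant. SAP section 8 lists the changes from the protocol, and the loss of the testing order is not among them.

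**The concern.** A stop-at-first-failure sequence is well defined only when each step yields one decision. Here several steps yield many p-values, and neither document says which visit counts, in what order visits are taken, or how many must be significant. Whoever programs the analysis has to choose, and the choices differ greatly in error rate and in how far the sequence gets.

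The order raises a second question. If 2.2.2 and 2.2.3 form one chain, an induction endpoint at Week 16 can be claimed only after success at Week 52. That does not fit a plan in which the two phases are concluded separately.

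At stake are the secondary claims. The co-primary tests do not depend on this order.

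**Working it through.** **1. The plan's own figures.** The documents give no error rate or power for the hierarchy, so the co-primary figures serve as the anchor. The test level comes from Protocol 8.6.1: "Each null hypothesis of no difference will be rejected if the resulting p-value for the respective statistical test is less than 0.05". The rates come from 8.2: "Expected rates for induction of clinical remission with endoscopic response at Week 16 are 40% for placebo and 55% for Rifaximin DR". With pooled variance and a two-sided 0.05 test:

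z = [0.15·√240 − 1.96·√(2·0.475·0.525)] / √(0.40·0.60 + 0.55·0.45) = (2.324 − 1.384)/0.698 = 1.35, so power is 91.1%.

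This agrees with "a sample size of approximately 240 subjects per treatment group will have at least 90% power". For both endpoints, 0.911² = 83% if independent, which fits "Approximately 80% power is available to detect significant differences between Rifaximin DR and placebo for both co-primary endpoints".

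**2. P-values per step.** Protocol 3.1 gives 14 post-baseline visits through Week 52: Weeks 2, 4, 8, 12, 16, then nine more at four-week intervals. IBDQ and WPAI are collected post-baseline at Weeks 16, 28, 40 and 52 (6.1.4 to 6.1.6). Markers are collected at Visits 7 and 16 (6.3.2, 6.3.3).

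| Step, in listed order | p-values |
|---|---|
| Week 52 pair | 2 |
| CDAI < 150 at Week 16 | 1 |
| Symptom remission over time | 1 |
| Durable stool; durable pain | 1 + 1 |
| Pain response; stool response | 14 + 14 |
| SES-CD change (Weeks 16, 52) | 2 |
| SES-CD of 0 | 1 |
| CDAI remission by visit | 14 |
| Time to loss of CDAI response | 1 |
| CDAI clinical response by visit | 14 |
| Two time-to-remission endpoints | 1 + 1 |
| IBDQ + four WPAI scores: 5 × 4 visits | 20 |
| Markers: up to 9 × 2 visits (8 named in blood, plus calprotectin) | 18 |

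The total is about 106 p-values in 16 steps.

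**3. If a step passes on any significant visit.** For a step null at all 14 visits, independence gives 1 − 0.95¹⁴ = 51%. With correlated normal test statistics, simulation gives 24% to 46% for AR(1) correlation 0.9 down to 0.5, and 14% to 35% for exchangeable correlation 0.9 down to 0.5. The correlations are assumptions. These figures apply to one null step, given that the chain has reached it.

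**4. If visits are taken in order, or all are required.** The error rate stays at 5%. The cost depends on onset, which the documents do not give. Assume placebo at 40%, a 15-point effect rising linearly from zero, 240 to 330 per arm, and AR(1) correlation 0.5 to 0.9:

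| Effect complete by | Chance of passing all 14 visits |
|---|---|
| Week 2 | 40% to 88% |
| Week 4 | 18% to 48% |
| Week 8 | 5% to 16% |
| Week 16 | 1% to 6% |

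Example for the last row: at Week 2 the effect is 15 × 2/16 = 1.875 points. With 330 per arm the standard error is √[(0.40·0.60 + 0.41875·0.58125)/330] = 0.0383. The mean z is therefore 0.49, and the chance of p < 0.05 at that first visit is about 8%. SES-CD change, including Week 16, stands behind two such 14-visit steps.

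**5. The Week 52 gate under a single chain.** Protocol 8.2 assumes a 15-point Week 52 effect at 210 per arm but states no placebo rate. At an assumed 25%, power per test is 91.0%, and both pass with probability 0.910² = 83%. At 40% it is 87.1%, and 0.871² = 76%. Independence of the pair is assumed. So even with the planned effect, the Week 16 CDAI endpoint would be closed off 17% to 24% of the time by Week 52 results.

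**The case against.** The strongest reply is that the stopping rule, taken at its word, ends formal testing at the first non-significant p-value. No any-visit rule appears anywhere, and any fixed visit order keeps the error at 5%. That is correct. What is missing is the order within a step, not error control under every reading.

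A reader might infer that the plan's secondary error rate is 14% to 51%. The documents do not support that. If the drug has no effect on any endpoint, the whole chain opens only when both Week 52 tests are significant, which has probability at most 5%, so a false claim anywhere in a single chain is also at most 5%. The larger figures need real effects on all earlier steps and a null step behind them. Even then, all 14 visits null is an extreme case: the pain step is reached only after durable pain response has passed, and CDAI remission by visit only after CDAI remission at Week 16, one of its own visits. Fewer null visits give smaller figures. With four null visits and independence, for instance, 1 − 0.95⁴ = 19%.

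A reader might also infer that the order must either stop early or lose error control. That is too absolute, because with full effect from Week 2 the strict reading can pass all 14 visits with probability up to 88%.

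Nor is the single chain certain. Section 8.7.5 speaks of the order for both phases, and two phase-specific sequences would fit that wording. Neither is written out, however, and 2.2.3 mixes the phases in one list.

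Finally, the SAP omits the hierarchy, makes secondary endpoints descriptive if the primary fails, and says both studies will end early. This limits the practical effect but does not settle the matter. If the primary succeeds, the SAP tests the same items with no order, and the protocol's order cannot be executed.

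**Conclusion.** The point stands in a limited form. The protocol's secondary order is incomplete as a testing procedure: four items carry 14 p-values each, SES-CD change carries two, IBDQ/WPAI about 20 and the markers up to about 18, with no rule for passing a step. A chronological or all-visits rule holds 5% but is likely to stop early if the effect builds gradually: a 1% to 16% chance of passing all 14 visits when the effect is complete at Week 8 or Week 16, under the assumed onset and correlations. An any-visit rule would not hold 5% within a truly null step behind real effects.

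Read literally as one chain, the order also makes a Week 16 endpoint depend on Week 52, in conflict with the independence of the two phases stated in the same section. The SAP removes the order without declaring it and keeps the tests. This should be corrected, but it bears on secondary claims only.

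**What to change.** Before unblinding, state in SAP 7.11, and correspondingly in Protocol 8.7.5, two fixed sequences at 0.05 per indication:

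- Induction, opened by the Week 16 co-primaries.
- Long term, opened by the Week 52 pair.

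Each later step should name one prespecified visit and one score. The sponsor chooses which endpoints fill the steps. Report all other visits, WPAI domains and markers descriptively, and list the change in SAP section 8. Restoring the protocol order to the SAP unchanged would not solve the problem.

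The cost is a short paragraph in the SAP and matching text in the protocol. The real price is fewer secondary endpoints that can be formally tested.

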#### **8.7.6      Use of an Efficacy Subset of Subjects**

The primary efficacy endpoint will be analyzed using the ITT Population.

#### **8.7.7      Exploration of the Effects of Various Prognostic Factors on Efficacy**

This study is not formally intended to obtain data on the influence of demographic and baseline disease characteristics (e.g., gender, race, age, and region (US/ROW)) on efficacy outcomes by the explicit design or randomization. However, the potential influence of these

**Confidential**

---

factors in efficacy outcomes will be investigated by pooled analysis across the two identical studies (RECD3125 and RECD3126, reference: FDA ISE guidance document).

#### **8.7.8 Criteria for Stopping the Study**

It is expected that the study will be terminated when the enrollment goals are reached. It is not anticipated that the study will be stopped early for any reason.

Confidential

---

## **9.0 STUDY ADMINISTRATION**

### **9.1 Investigator Information and Training**

The investigators and essential support staff will be trained by Salix (or designee) in regards to Good Clinical Practices (GCPs) and all aspects of protocol execution. It is the responsibility of the investigator to train ancillary study staff.

### **9.2 Monitoring**

This study will be monitored by Salix (or designee), in accordance with GCPs and applicable regulations. By signing this protocol, the investigator agrees to periodic, on-site monitoring of all appropriate study documentation.

The progress of the study will be monitored by periodic on-site visits and frequent communications between the Salix (or designee) and the investigator (either by phone, fax, email, or post).

During these contacts, the monitor will:

- Check and assess the progress of the study.
- Review study data collected.
- Conduct source document verification.
- Identify any issues and address their resolution.

The objectives of monitoring procedures are to verify that data are authentic, accurate, and complete; that the safety and rights of subjects are being protected; and that the study is conducted in accordance with the currently approved protocol (and any amendments), GCPs, and all applicable regulatory requirements.

### **9.3 Audits**

At its discretion, Salix (or designee) may conduct a quality assurance audit of this study. If such an audit occurs, the investigator agrees to allow the auditor direct access to all relevant documents and to schedule his/her time and the time of his/her staff to permit meetings with the auditor to discuss findings and any relevant issues.

In addition, regulatory agencies may conduct a regulatory inspection of this study. If such an inspection occurs, the investigator agrees to allow the inspector direct access to all relevant documents and to schedule his/her time and the time of his/her staff to permit meetings with the inspector to discuss findings and any relevant issues. The investigator will notify Salix immediately when a Regulatory Agency notifies the site of an inspection.

Confidential

---

## 10.0 ETHICAL AND LEGAL ASPECTS

The investigator and the study staff are responsible for conducting this study in accordance with the applicable principles which have their origins in the Declaration of Helsinki, ICH, GCPs, and all other applicable laws and regulations.

### 10.1 Institutional Review Board/ Independent Ethics Committee (IRB/IEC) Approval

This protocol, the informed consent form, relevant supporting information, and all types of subject recruitment or advertisement information must be approved by the appropriate IRB/IEC before the study is initiated. Any amendments to the protocol must also be approved, where necessary, by the IRB/IEC prior to implementing changes in the study. Documentation of these approvals must be provided to the sponsor prior to the initiation of the amendment.

The investigator's responsibilities regarding the IRB/IEC are as follows:

- Obtain IRB/IEC approval of the protocol, informed consent form, and any advertisements for subject recruitment prior to their use.
- Obtain IRB/IEC approval for any protocol amendments and revisions to the informed consent document before implementing the changes.
- Provide the IRB/IEC with any required information before or during the study.
- Submit progress reports to the IRB/IEC, as required, during the conduct of the study; request re-review and approval of the study, as needed; provide copies of all IRB/IEC re-approvals and relevant communication to the sponsor.
- Notify the IRB/IEC within 10 days (unless required sooner by IRB/IEC) of all serious and unexpected AEs related to the study medications that are reported to you by the sponsor. The investigator is responsible for updating the IRB/IEC on the progress of the study and of any changes made to the protocol at least once a year or at regular intervals as deemed appropriate. The investigator must also keep the IRB/IEC informed of any AEs, according to the IRB/IEC policy.

Notifying Salix within 24 hours of awareness and the IRB/IEC within 10 days (unless required sooner by IRB/IEC) of all unanticipated problems involving risk to subjects or others. **For the purposes of this study, an Unanticipated Problem is defined as any incident, experience, or outcome that meets all of the following criteria:**

- Unexpected in nature, severity, or frequency (i.e. not described in study-related documents such as the IRB-approved protocol or consent form, the investigators brochure, etc.)
- Related or possibly related to participation in the research (i.e. possibly related means there is a reasonable possibility that the incident experience, or outcome may have been caused by the procedures involved in the research)

